2.3 Staging process

Participating PBCRs will assign tumour stage at diagnosis using the Toronto Guidelines (TG) supported by the detailed guidance based on the Australian experience being produced as a study document [8] and translated in French, Spanish, Portuguese and Italian. The TG includes a two-tiered system to define stage [5,8]: Tier 2 staging system is more detailed and intended for use in high resource settings. The full details of Tier 1 and Tier

2 staging criteria for each tumour type are available elsewhere [8]. All PBCRs are asked to provide Tier 2 stage if they can access the clinical details, otherwise Tier 1 will be acceptable for the primary endpoints of only assessing the proportions of localised vs metastatic tumour at diagnosis. Registries will provide pseudo-anonymised descriptive information at an individual patient level. It is also asked to collect information regarding the clinical data sources for staging and the examinations performed (e.g., CT scan of chest versus Chest X-ray).

To assure registry standardisation, a two-step process is proposed. First, a training session to introduce TG and second, the creation of a quality assurance set of fictitious cases to analyse how well standardised the application of the TG is between registries.

2.3.1 General rules of staging

Toronto stage is defined as extent of disease at the time of diagnosis and is based on evidence acquired before treatment. The only exceptions are:

- Staging of localised (non-metastatic) Wilms tumour resected after pre-operative (neo-adjuvant) chemotherapy, where stage is based on surgical and pathological assessment of the nephrectomy specimen and indicated by the prefix 'y'.
- Investigations performed to exclude distant metastases might be used if they occur within a short time after surgery to the primary tumour, providing it is before any systemic therapy is started.

For rhabdomyosarcoma, tumour stage should always be defined at diagnosis according to standard clinical TNM rules with nodal involvement assessed by imaging and/or lymph node biopsy, if performed prior to chemotherapy.

For all diagnostic groups including Wilms tumour, the presence of distant metastases is assessed clinically (including imaging) or pathologically at the time of diagnosis and before neoadjuvant therapy. Metastases are defined at diagnosis.

Further details are provided in Appendix.

2.3.2 Quality assurance of implementing Toronto staging

This research project will take a proactive stance towards standardisation on how different registries implement collection of stage according to the Toronto consensus guidelines.

We will:

- Maintain close liaison with ongoing international efforts to build an e-tool available to all PBCRs (this may occur as part of ENCR/JRC standard practice for the European Cancer Information System based at the European Commission's Joint Research Centre (JRC), Ispra <https://ecis.jrc.ec.europa.eu/>), as they are actively working to have the Toronto guidelines included in the electronic cancer staging tool for PBCRs personnel training.
- Create an anonymized set of real or fictional cases with source material and require all participating registries to stage these according to their processes.
- Hold on-line training workshops for all participating registry staff. Note that some have been held already in Nov 2020 as part of regular training for registries in childhood cancers by the European School of Oncology (ESO) and are available on-line.

- 1st event, 12 Nov 2020,
 - <https://www.e-eso.net/sessions/1727>
 - 2nd event, 19 Nov 2020,
 - <https://www.e-eso.net/sessions/1728>
- Furthermore, encourage the use of a tool to facilitate the definition of stage by registrars for all cancer sites including the Toronto stage for paediatric cancers. This tool is available on-line at https://canstaging.org/tool?tnm_version=Toronto. The tool was developed by a collaboration between the Northern Ireland Cancer Registry (NICR), the International Agency for Research on Cancer (IARC), the Union for International Cancer Control (UICC), and Cancer Council Queensland (CCQ).

2.4 Structure of the case record to be submitted

For each tumour we will send a record template in Excel including the *compulsory* and the *optional* variables in one sheet and in a separate sheet the record template including the required and mandatory *additional indicators and information*. The PBCRs have to complete it according to the structure and the variables definitions indicated in Table 2 and described below.

2.4.1 Compulsory variables

Each record (case) includes demographic variables such as sex, year of birth, age at diagnosis in months, basis of diagnosis, plus information on examinations and the data sources used by the registrars for staging (see structure of the record, Table 2). If the tumour is a second or a third tumour, this fact should be reported. We ask to specify the International Classification of Childhood Cancers (ICCC-3) classification of previous tumours and the corresponding year of diagnosis. Tumour stage should be assigned by the PBCRs according to the Toronto consensus staging guidelines and associated implementation tools. PBCRs should use all available hospital data sources and procure input from relevant clinical staff when required to ensure consistent clinical interpretation of diagnostic investigations. Follow-up data (life status and time in days from diagnosis to death or last follow up) might be sent separately and at a later timepoint to ensure maximum completeness of follow up information.

2.4.2 Optional variables

In the JARC Pilot Study, the availability of information on **first line of treatment and recurrence or relapse** was already tested [7]. The JARC study showed that almost all participating PBCRs were able to collect this data item for both cancers. Furthermore, for treatment, if we exclude two countries that were not able to provide this information, 95% of Neuroblastoma and 84% of Wilms' cancer patients would have complete information. For those patients that had chemotherapy or radiotherapy, radiotherapy field and drug names were frequently reported for neuroblastoma. For Wilms tumour, these percentages were similar for the drug names but lower for the radiotherapy field (74%).

This project will therefore test how much information registries currently hold on these two important factors across all six tumour types (see Table 2). The rationale for collection of these additional variables is a feasibility assessment of how complete and with how much effort these additional factors can be provided by PBCRs. We will use this information for descriptive analysis of data availability, quality and completeness across the participating regions. The PBCRs are requested to report only the treatments included in the patient's planned

first line therapy. If a registry is not able to identify what is first line therapy, we recommend including all treatments given in the first 12 months following the date of diagnosis.

Knowledge of relapse/recurrence or progression of the disease is important for understanding the success of first line therapy. The latter is decided according to initial tumour stage and presence of other non-stage prognostic factors and requires data on relapse/recurrence or progression. We therefore ask PBCRs able to collect data on relapse/recurrence/progression to do so in order to understand the feasibility of this data item collection. It should be collected for all cases within the 3 years of follow-up.

Some **non-stage prognosticators** (NSP) for medulloblastoma, rhabdomyosarcoma, neuroblastoma and Wilms tumour are also requested if available [9]. No NSPs are currently recommended for collection for osteosarcoma and Ewing sarcoma. According to the JARC pilot study, for most registries the major source available for stage reconstruction was the clinical record of major hospital admissions, indicating NSP should be available for retrieval.

Even if they are not the major objective of the study, NSPs are important to better understand survival differences, as they characterize the behaviour of the tumour and are crucial for clinical risk stratification for treatment. Registries are asked whether it is possible for them to collect these items. Furthermore, **cause of death**, categorised as due to tumour, or toxicity, or comorbidity or other cause, is another optional variable. This categorization requires a clinical review of the information reported to the PBCR on causes of death, which may be multiple. This collection is also important to understand the feasibility of future specific studies that would test the hypothesis that there may be differences between countries in proportion of deaths ascribed to toxicity of treatment.

2.4.3 Additional indicators and information

2.4.3.1 Time taken to assign Toronto stage

We ask all PBCRs to send us an estimate of the additional effort (in approximate average minutes/case) currently required by the registry to obtain the Toronto stage for each specific tumour type.

2.4.3.2 Quality indicators

All PBCRs are required to submit in a default excel file the:

- % DCO (death certificate only) cases in the PBCR in the study period (calculated as: the number of children diagnosed by DCO, or autopsy/ number of children diagnosed with cancer)
- % NOS (not otherwise specified) in brain for children in the selected period: Number of morphology NOS in the brain (ICCC 3rd ed. III f) / number of cases in brain (ICCC 3rd ed. III)
- % NOS in kidney for children in the selected period: Number of morphology not otherwise specified in the kidney (ICCC 3rd ed. VI c) / number of cases in kidney (ICCC 3rd ed. VI)
- % NOS in soft tissue sarcomas (STS) for children in the selected period: Number of morphology NOS in the STS (ICCC 3rd ed. IX e) / number of cases in STS (ICCC 3rd ed. IX).
- %NOS in Bone Tumours for children in the selected period: Number of Unspecified malignant bone tumours (ICCC 3rd ed. VIII e) / number of cases with bones tumours (ICCC 3rd ed. VIII)
- % of neuroblastoma of the unknown primary sites: Number of neuroblastoma (ICD-O M-9500/3) and ganglioneuroblastoma (ICD-O M-9490/3) in C80.9 (unknown primary sites)/ ICC 3rd ed IV a.

2.5 Identification of registries

All the European population-based registries have been invited to participate in the study. In addition, other non-European registries including Australia, Canada (Ontario), Brazil, Japan and Boston (USA) were invited as they are known to have the capability to reconstruct the requested Toronto stage and other prognostic variables. The 15 European countries who contributed data to the JARC pilot study [7], those who attended the JARC pilot study workshop held in Brussels - March 2018, have assured their participation. Both at the Brussels meeting and through the JARC study, registries stated that they could apply the Toronto consensus guidelines for tumour staging to their existing data, using their online and usual sources of data such as the pathological file and the hospital discharge administrative files. For a variable number of cases, the clinical hospital record is available as well. Also, all registries included in the EURO CARE-6 study (30 countries) have been invited to contribute.

Participating cancer registries will be population-based, either paediatric or general. Almost all the registries participating have already been checked by different stakeholders (organisation or specific project such as: IARC (<https://iicc.iarc.fr/>), ENCR, EURO CARE (<http://www.eurocare.it/>), ACCIS (<https://accis.iarc.fr/>) for quality indicators and this assures the expected completeness and quality of the information they collect for incidence and survival. There are a few exceptions among the PBCRs (Finland, Japan and Poland) and new checks will be carried out to ensure the coverage of these specific registries.

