2.8 Statistical considerations

The main endpoints for the statistical analyses, by tumour type, are:

1. Differences in stage distribution between countries/regional groupings.
2. Survival differences between countries/regional groupings, and how much of any difference is explained by variations in stage distribution and/or survival by stage.

The formal statistical power to detect differences in stage distribution and survival rates between countries is necessarily limited by incident numbers of each of the six tumour types per country over the recent time period for which PBCRs are able to provide tumour stage. Therefore, analyses of stage distribution and survival rates for each tumour type per country will be descriptive, with 95% confidence intervals reported.

Approximately 8,000 cases will be included (table 2). As the study is population-based, these are the largest numbers available and are not biased in the ways that might affect institutional or clinical trial series.

Endpoint 1: To formally assess if differences in tumour stage at diagnosis are significant, we will group European countries according to the regional geographies used in EURO CARE 5 to achieve the group sizes necessary. Non-European jurisdictions will be considered individually. For expected case numbers by registry (table 2), we have approximately 60% power to detect a 10% difference in lower stages (localised, loco-regional) versus more advanced stage (metastatic) between two countries or regional groupings where there are 250 cases of each tumour type in each group (medulloblastoma, Wilms tumour). For group sizes with 300 cases (neuroblastoma), the power would be 70%. We will combine the sarcomas, who collectively comprise 29% of the cohort, for assessment of differences in stage distribution at diagnosis, according to the same country groupings.

Endpoint 2: Overall survival for each tumour type will be analysed for all patients and broken down by appropriate tumour stage, using standard Kaplan-Meier methods reported with 95% CIs. Survival differences between countries/regional groupings and how much is explained by variations in stage distribution will be studied by multivariable Cox regression including stage and other relevant prognostic variables (age at diagnosis, sex and/or primary site for at least some diagnostic groups), and confounders including stage migration.

3. Oversight and funding of the project

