CT/ MRI primary site	1	Y/N/unknown 1/0/9
MRI whole neuraxis	1	Y/N/unknown 1/0/9
MRI whole neuraxis outcome		Negative/Positive/Suspicious/Unknown 0/1/2/9
CT thorax	1	Y/N/unknown 1/0/9
CT thorax outcome		Negative/Positive/Suspicious/Unknown 0/1/2/9
Imaging of regional lymph nodes	1	Y/N/unknown 1/0/9
Imaging of regional lymph nodes outcome		Negative/Positive/Suspicious/Unknown 0/1/2/9
CSF	1	Y/N/unknown 1/0/9
CSF outcome		Negative/Positive/Suspicious/Unknown 0/1/2/9
MIBG scan	1	Y/N/unknown 1/0/9
MIBG scan outcome		Negative/Positive/Suspicious/Unknown 0/1/2/9
Abdominal ultrasound	1	Y/N/unknown 1/0/9
Abdominal ultrasound outcome		Negative/Positive/Suspicious/Unknown 0/1/2/9
Bone scan	1	Y/N/unknown 1/0/9
Bone scan outcome		Negative/Positive/Suspicious/Unknown 0/1/2/9
Bone marrow aspirate or biopsy	1	Y/N/unknown 1/0/9

Bone marrow aspirate or biopsy outcome		Negative/Positive/Suspicious/Unknown 0/1/2/9
x-ray thorax	1	Y/N/unknown 1/0/9
x-ray thorax outcome		Negative/Positive/Suspicious/Unknown 0/1/2/9
PET	1	Y/N/unknown 1/0/9
PET outcome		Negative/Positive/Suspicious/Unknown 0/1/2/9
Tissue biopsy	1	Y/N/unknown 1/0/9
Tissue biopsy outcome		Negative/Positive/Suspicious/Unknown 0/1/2/9
Source used for staging		
Clinical report (hospital clinical records)	1	Y/N/unknown 1/0/9
Pathological report	1	Y/N/unknown 1/0/9
Administrative files (hospital discharge, etc.)	1	Y/N/unknown 1/0/9
Clinical study group	1	Y/N/unknown 1/0/9
Others (string)	10	alphabetic
Toronto staging, Neuroblastoma		
Stage Tier 1	2	L/LR/M/MS/X 1/2/3/4/9
Stage Tier 2	2	L1/L2/M/MS/X 1/2/3/4/9
Laterality	1	Not applicable/Right/Left/Unilateral NOS/Bilateral//unknown 0/1/2/3/4/9
* NSP: N-Myc	1	Amplified Y/N (exact definitions to be discussed)
Toronto staging, Wilms tumour		
Stage Tier 1 after pre-surgery chemotherapy	1	L/M/X 1/2/9
Stage Tier 2 after pre-surgery chemotherapy	1	y-I/y-II/y-III/IV/9 1/2/3/4/9
Stage Tier 1 after immediate surgery (i.e., surgery first)	1	L/M/X 1/2/9
Stage Tier 2 after immediate surgery	1	I/II/III/IV/X 1/2/3/4/9
Laterality	1	R/L/B 1/2/3
O_NSP: Wilms Presence of anaplasia	1	No/Yes, but unknown if focal or diffuse/Yes, focal/Yes, diffuse/ Anaplasia unknown 0/1/2/3/9
Toronto staging, Medulloblastoma		
Stage Tier 1	1	L/M/X 1/2/9
Stage Tier 2	2	M0/M1/M2/M3/M4/X 0/1/2/3/4/9
* Evaluation of postoperative residual disease		R0/R1/R2/R+/unknown 0/1/2/3/9
*_NSP: Wingless (WNT) medulloblastoma	1	Y/N/unknown 1/0/9
*_NSP: Sonic Hedgehog (SHH) medulloblastoma	1	Y/N/unknown 1/0/9

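### Staging source and work-up are recorded for each case but have no stated role in the Endpoint 1 regional comparison, so unequal record access could be read as late diagnosis

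*Protocol*

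**What the plan says.** **Staging rule.** Under section 2.3.1, for all tumour types, "the presence of distant metastases is assessed clinically (including imaging) or pathologically at the time of diagnosis and before neoadjuvant therapy".

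**Sources.** Section 2.5 reports what registries said about feasibility: they could apply the guidelines to existing data "using their online and usual sources of data such as the pathological file and the hospital discharge administrative files". It continues: "For a variable number of cases, the clinical hospital record is available as well". Section 2.4.2 says of the pilot that "for most registries the major source available for stage reconstruction was the clinical record of major hospital admissions". Section 2.4.1 instructs: "PBCRs should use all available hospital data sources and procure input from relevant clinical staff when required".

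**What is collected.** Section 2.4.1 lists as compulsory "plus information on examinations and the data sources used by the registrars for staging". Table 4 (Structure of the record) has coded yes/no/unknown fields for clinical report, pathology report, administrative files and clinical study group. It also has fields for individual examinations, nearly all with a negative/positive/suspicious/unknown outcome. None of these carries the optional mark. An X (unknown) stage code exists for each tumour.

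**What is analysed.** Section 2.8, Endpoint 1: "To formally assess if differences in tumour stage at diagnosis are significant, we will group European countries according to the regional geographies". The contrast is localised or loco-regional against metastatic. Neither the source fields nor the examination fields are mentioned. Covariates and stage migration are named only for the Endpoint 2 Cox model. The quality indicators in sections 2.4.3.2 and 2.7 cover death-certificate-only cases, microscopic verification, unspecified morphology and follow-up, not staging source.

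**How a difference will be read.** Section 1 presents Hypothesis 1 as a test for late diagnosis. It traces a stage difference to awareness, child health systems or delay after referral.

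**The concern.** Recording a metastasis needs one positive entry. Excluding one needs evidence that someone looked and found nothing. A registry that works from fewer documents may hold the first kind of evidence more often than the second, and may miss some positive entries too. If the share of cases staged this way differs between regions, the recorded metastatic share can differ when the true share does not. This is a matter of access to records and could arise even if every country did the same imaging.

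The direction is awkward for Hypothesis 1. The region with poorer access would appear to diagnose earlier, and the region with fuller records would appear late. The error would also carry into Endpoint 2, because unrecognised metastatic cases counted as localised lower survival in the localised group. The protocol holds the data needed to examine this but does not say that they will be used, and its list of explanations leaves the possibility out.

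**Working it through.** **1. The plan's own figure.** Section 2.8 states about 60% power for a 10-point difference with 250 cases per group, and 70% with 300. Test level and baseline share are not given. I assume a two-sided 5% pooled two-proportion test, with power = Φ[(d − 1.96·s0)/s1], s0 = √(2p̄(1−p̄)/n) and s1 = √((p1(1−p1)+p2(1−p2))/n). For 40% against 50% and n = 250: s0 = 0.0445, s1 = 0.0443, (0.10 − 0.0872)/0.0443 = 0.29, power 61%. For n = 300 it is 69%. The figures reproduce at a baseline near 40 to 50% and are not in dispute. They supply the yardstick: 10 points.

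**2. Model for unequal access.** All inputs are assumptions; the documents give none of them.
- P: true metastatic share, the same in both groups.
- f: share of group B staged from limited sources (group A: none).
- Se: proportion of metastases found in those cases.

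Observed share in B = P[1 − f(1 − Se)]. False difference = P·f·(1 − Se). If group A also has a share fA staged this way, the difference becomes P(1 − Se)(f − fA), so only the inequality between groups matters.

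Worked case, P = 40%, f = 0.5, Se = 80%: observed 0.40 × (1 − 0.5 × 0.2) = 36%, a false difference of 4 points. With n = 250, s0 = s1 = 0.0434. Then (0.04 − 0.0851)/0.0434 = −1.04, or 14.9%. The other tail adds 0.2%, giving 15%.

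**3. Range, 250 per group, no true difference.** The nominal rate is 5%.

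| P | f | Se | False difference (points) | Chance of p < 0.05 |
|---|---|---|---|---|
| 20% | 0.25 | 90% | 0.5 | 5% |
| 40% | 0.25 | 90% | 1.0 | 6% |
| 40% | 0.25 | 80% | 2.0 | 7% |
| 30% | 0.5 | 80% | 3.0 | 12% |
| 40% | 0.5 | 80% | 4.0 | 15% |
| 50% | 0.5 | 80% | 5.0 | 20% |
| 40% | 1 | 80% | 8.0 | 46% |
| 50% | 1 | 80% | 10.0 | 61% |

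The last two rows need a whole regional group with no clinical records. With lower sensitivity a large effect needs less: P = 30%, f = 0.75, Se = 60% gives 9 points and 64%.

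**4. Carry-over to survival by stage.** In the worked case, 64 of every 100 cases in B are recorded as localised, and 4 of them are truly metastatic: 4/64 = 6%. If those cases survive like other metastatic cases, localised survival in B falls by about one sixteenth of the survival gap between the two stages.

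**5. Would the planned safeguards catch it?** Training and common test cases (section 2.3.2) come with source material supplied, so they test how the rules are applied, not which real documents a registry can reach. The instruction to use all available hospital sources does not equalise what is available. The 97% stage completeness reported from the pilot covers two tumours; it shows that a stage was assigned, not on what evidence.

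**The case against.** Much can be said for the plan.

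- **The point rests partly on silence.** Section 2.8 names no test or model for Endpoint 1. A reader might infer that the comparison is unadjusted and disregards the source fields. The text does not say so, and a statistical analysis plan that is not shown may use them. What stands is that the protocol itself fixes the reading of a difference in section 1 and leaves ascertainment out.
- **Section 2.5 gives an open list.** A reader might infer that registries stage only from pathology and discharge files, or that such files cannot show a metastatic work-up. The protocol says neither. The two files are examples, the pilot found the clinical record to be the major source for most registries, and section 6 commits the working group to help with access to clinical and hospital data. Access is therefore better than a bare reading of section 2.5 suggests, but most is not all, and the protocol itself calls availability variable.
- **The record can identify the doubtful cases.** The examination outcome fields show whether a localised case has a documented negative work-up. This is right, and it makes them a better marker than document source alone. It is also why giving them no stated role is a missed opportunity.
- **X against L may be settled elsewhere.** Full staging criteria are in a manual and appendix not shown, X codes exist, and section 2.2 requires cases with scarce information to be kept. So this is something to confirm, not an error.
- **A restricted set is itself selected.** Limiting the analysis to well-documented cases gives up some of the population coverage that section 2.8 claims as a strength. This stands in full: such an analysis can support the main result but cannot decide it.

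**Conclusion.** The point holds as a gap in interpretation and sensitivity analysis. Registries differ in access to clinical records. The protocol collects source, examinations and outcomes but gives them no stated role in the formal Endpoint 1 comparison, and it does not list ascertainment among the explanations of a stage difference. Followed as written, unequal access could be read as late diagnosis.

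The size cannot be computed from the documents. Under the assumptions shown it runs from negligible (0.5 points, error rate about nominal) through several points, with the largest values needing very unequal access or low sensitivity. A reader might take the 46% or 61% as the expected false-positive rate, or conclude that registries without clinical records will under-record metastases. Neither is supported: prevalence, the share with limited sources and sensitivity are all assumed, and group A is given perfect ascertainment. A cheap improvement is warranted; the documents do not show that the comparison is invalid.

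**What to change.** In section 2.8, Endpoint 1:

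(a) Tabulate, by region and tumour type, the staging source and the share of localised cases with a documented negative metastatic work-up.

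(b) Repeat the regional stage comparison, and survival by stage, in cases with a clinical report, a clinical study group source or a documented metastatic work-up. Report this as a sensitivity analysis beside the all-case result.

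(c) In section 1, add differential ascertainment to the explanations of a stage difference. State that a regional difference which shrinks materially or reverses in (b) will not be attributed to late diagnosis without discussing ascertainment.

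Separately, confirm that the staging manual codes cases with no evidence on metastases as X, and refer to that rule in section 2.3.1.

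Cost: one table, one repeated analysis and a few sentences. No new data are needed, since the fields are already in Table 4. The restricted set will be smaller and selected on record access, with wider intervals, and is therefore supportive only.
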